12. Has known active central nervous system (CNS) metastases and/or carcinomatous meningitis or leptomenigeal disease. Subjects with previously treated brain metastases may participate provided they are stable (without evidence of progression by imaging for at least four weeks prior to the first dose of trial treatment and any neurologic symptoms have returned to baseline), have no evidence of new or enlarging brain metastases, and are not using steroids for at least 7 days prior to trial treatment. This exception does not include carcinomatous meningitis which is excluded regardless of clinical stability.
13. Concomitant (or receipt of) treatment with medications that may affect the metabolism of pembrolizumab and/or axitinib within 7 days prior to Cycle 1, day 1 of axitinib.
14. Has received a live vaccine within 30 days of planned start of study therapy. Note: Seasonal influenza vaccines for injection are generally inactivated flu vaccines and are allowed; however intranasal influenza vaccines (e.g., Flu-Mist®) are live attenuated vaccines, and are not allowed.
15. Is pregnant or breastfeeding, or expecting to conceive or father children within the projected duration of the trial, starting with the pre-screening or screening visit through 120 days after the last dose of trial treatment.
16. Any uncontrolled, intercurrent illness including but not limited to ongoing or active infection, symptomatic congestive heart failure, unstable angina pectoris, cardiac arrhythmia
17. Prolonged QTc interval on Screening EKG >475 ms.
18. Ejection Fraction <40% by 2D ECHO at Screening.
19. Any serious medical or psychiatric illness/condition including substance use disorders likely in the judgment of the Investigator(s) to interfere or limit compliance with study requirements/treatment.
20. Has active autoimmune disease that has required systemic treatment in the past 2 years (i.e. with use of disease modifying agents, corticosteroids or immunosuppressive drugs). Replacement therapy (eg., thyroxine, insulin, or physiologic corticosteroid replacement therapy for adrenal or pituitary insufficiency, etc.) is not considered a form of systemic treatment.

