#### 8.4.1 Concurrent Medications

Because there is a potential for interaction of axitinib with other concomitantly administered drugs through the cytochrome P450 system, the case report form must capture the concurrent use of all other drugs, over-the-counter medications, or alternative therapies. The PI should be alerted if the patient is taking any agent known to affect or with the potential to affect selected CYP450 isoenzymes. Appendix E presents guidelines for identifying medications/substances that could potentially interact with the study agent, axitinib. CYP3A4/5 substrates are allowed as concomitant medication at physician discretion and will not be exclusionary for study participation.

**Strong CYP3A4/5 Inhibitors**: The concomitant use of strong CYP3A4/5 inhibitors should be avoided (e.g., ketoconazole, itraconazole, clarithromycin, atazanavir, indinavir, nefazodone, nelfinavir, ritonavir, saquinavir, telithromycin, and voriconazole). Selection of an alternate concomitant medication with no or minimal CYP3A4/5 inhibition potential is recommended. Although axitinib (INLYTA®) dose adjustment has not been studied in patients receiving strong CYP3A4/5 inhibitors, **if a strong CYP3A4/5 inhibitor must be co-administered, a dose decrease of INLYTA by approximately half is recommended**, as this dose reduction is predicted to adjust the axitinib area under the plasma concentration vs time curve (AUC) to the range observed without inhibitors. The subsequent doses can be increased or decreased based on individual safety and tolerability. If co-administration of the strong inhibitor is discontinued, the INLYTA dose should be returned (after 3 – 5 half-lives of the inhibitor) to that used prior to initiation of the strong CYP3A4/5 inhibitor.

**Strong CYP3A4/5 Inducers:** The concomitant use of strong CYP3A4/5 inducers should also be avoided (e.g. rifampin, dexamethasone, phenytoin, carbamazepine, rifabutin, rifapentin, phenobarbital and St. John's wort). Selection of concomitant medication with no or minimal CYP3A4/5 induction potential is recommended. Moderate CYP3A4/5 inducers (e.g. bosentan, efavirenz, etravirine, modafinil and nafcillin) should also be avoided if possible.

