### 9.1.3 Drug Metabolism, Pharmacokinetics and Toxicology

The population pharmacokinetic analysis pooled data from 17 trials in healthy subjects and patients with cancer. A two-compartment disposition model with first-order absorption and lag-time adequately describes the axitinib concentration-time profile.

Absorption and Distribution: Following single oral 5-mg dose administration, the median Tmax ranged from 2.5 to 4.1 hours. Based on the plasma half-life, steady state is expected within 2 to 3 days of dosing. Dosing of axitinib at 5 mg twice daily resulted in approximately 1.4-fold accumulation compared to administration of a single dose. At steady state, axitinib exhibits approximately linear pharmacokinetics within the 1-mg to 20-mg dose range. The mean absolute bioavailability of axitinib after an oral 5 mg dose is 58%.

Compared to overnight fasting, administration of INLYTA with a moderate fat meal resulted in 10% lower AUC and a high fat, high-calorie meal resulted in 19% higher AUC. INLYTA can be administered with or without food [*see Dosage and Administration (2.1)*].

Axitinib is highly bound (>99%) to human plasma proteins with preferential binding to albumin and moderate binding to  $\alpha$ 1-acid glycoprotein. In patients with advanced RCC (n=20), at the 5 mg twice daily dose in the fed state, the geometric mean (CV%) Cmax and AUC0-24 were 27.8 (79%) ng/mL and 265 (77%) ng.h/mL, respectively. The geometric mean (CV%) clearance and apparent volume of distribution were 38 (80%) L/h and 160 (105%) L, respectively.

Metabolism and Elimination: The plasma half life of INLYTA ranges from 2.5 to 6.1 hours. Axitinib is metabolized primarily in the liver by CYP3A4/5 and to a lesser extent by CYP1A2, CYP2C19, and UGT1A1. Following oral administration of a 5-mg radioactive dose of axitinib, approximately 41% of the radioactivity was recovered in feces and approximately 23% was recovered in urine. Unchanged axitinib, accounting for 12% of the dose, was the major component identified in feces. Unchanged axitinib was not detected in urine; the carboxylic acid and sulfoxide metabolites accounted for the majority of radioactivity in urine. In plasma, the N-glucuronide metabolite represented the predominant radioactive component (50% of circulating radioactivity) and unchanged axitinib and the sulfoxide metabolite each accounted for approximately 20% of the circulating radioactivity.

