## 10.2 Dose Titration Guidelines for Axitinib

All patients will begin therapy at the starting dose level of 5 mg PO twice daily. Patients will be evaluated closely during cycle 1 for adverse events, laboratory studies, and review of study diaries and blood pressure logs. Additionally, patients will be instructed to call with any adverse events between study visits. **If there is no grade 2 or greater toxicity on cycle 2 day 1, the patient will be eligible for dose escalation of axitinib as per Table 8. Dose escalation DURING a cycle is not permitted. Consideration of escalation should only be done on day 1 of all subsequent cycles. If a patient is dose-escalated on day 1, they should resume blood pressure monitoring daily during the first three weeks of that cycle until evaluated during week 4 (i.e. day 22) visit of that same cycle.**

Dose reductions for grade 2 or greater toxicities may be done at any time during the cycles as per the following guidelines, and Tables 8 and 9.

- For grade 2 or greater fatigue, hand-foot syndrome, mucositis, or diarrhea, attempt medical supportive care first: (topical creams, anti-diarrheal, magic mouthwash or similar).
- If no improvement within 3 days, dose reduce axitinib as per Table 8.
- Axitinib may be held for 3-5 days prior to dose reduction in the judgment of the treating investigator, particularly for grade 3 toxicities

Management of Axitinib-related Hypertension:

- Patients will be provided with blood pressure cuffs and monitoring sheets. They will be instructed to monitor their blood pressure once daily before the evening dose of axitinib. They are to notify the study team for BP  $\geq$  150/100 mm Hg or for BP  $\geq$  120/80 mm Hg with any symptoms perceived to be related to BP (headache, chest pressure, shortness of breath, dizziness, blurry vision).
- Medications are to be added and titrated aggressively. Preferred sequence as follows:
  - Calcium channel blockers: (amlodipine, nifedipine, diltiazem, etc.)
  - ACE inhibitors or ARB (lisinopril, valsartan, losartan, etc.)
  - Diuretics (hydrochlorothiazide, furosemide). Patient should be prescribed concurrent potassium and magnesium supplementation and scheduled for potassium and magnesium laboratory tests within three days of starting.
  - Avoid beta-blockers, clonidine, digoxin.
  - If BP still  $\geq$  150/100 mm Hg despite maximal doses of three anti-hypertensive medications, axitinib should be reduced by one dose level.

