### Diary Directions

Begin taking axitinib twice a day, (as your doctor has told you to during the study):

1. On the days that you are supposed to take axitinib – axitinib should be taken by mouth, twice a day on an empty stomach, approximately 12 hours apart with a glass of water.
2. You may take each dose with or without food. Do not chew or break tablets.
3. If a dose is missed you may take the missed dose if it has been less than 2 hours from your scheduled dose. Do not make up missed doses if it has been more than 2 hours from your scheduled dose.
4. If you vomit after a dose, do not take another dose. Take your next dose of the day at the same time you would normally take it.
5. Avoid taking grapefruit juice and St. John’s Wort.
6. Avoid smoking if you are taking axitinib because it may decrease the amount of the drug in your body.
7. Taking over-the-counter drugs to block stomach acid may interfere with the absorption of the study drug. Please avoid taking medications like omeprazole (Prilosec OTC) or cimetidine (Tagamet) unless you first discuss with your doctor.
8. Please bring the empty bottle or any leftover tablets and this diary to your next clinic visit.

**Patient Dosing Diary** Axitinib Dose Level: \_\_\_\_\_ mg twice a day  
**Patient Initials (L, F, M): Patient ID:** \_\_\_\_\_ **Cycle:** \_\_\_\_\_

This is a diary on which you are to **record the date, time and number of tablets you take each day on the days that you are supposed to take Axitinib**. You should take your scheduled dose of each tablet. If you forget to take a dose, please write "0", but remember to take your prescribed dose at the next regularly scheduled time.

Day	Date(s)	# of Tablets	Time Taken (Circle AM or PM)	# of Tablets	Time Taken (Circle AM or PM)
1			AM PM		AM PM
2			AM PM		AM PM
3			AM PM		AM PM
4			AM PM		AM PM
5			AM PM		AM PM
6			AM PM		AM PM
7			AM PM		AM PM
8			AM PM		AM PM
9			AM PM		AM PM
10			AM PM		AM PM
11			AM PM		AM PM
12			AM PM		AM PM
13			AM PM		AM PM
14			AM PM		AM PM
15			AM PM		AM PM
16			AM PM		AM PM
17			AM PM		AM PM
18			AM PM		AM PM
19			AM		AM

			PM		PM
20			AM PM		AM PM
21			AM PM		AM PM
22			AM PM		AM PM
23			AM PM		AM PM
24			AM PM		AM PM
25			AM PM		AM PM
26			AM PM		AM PM
27			AM PM		AM PM
28			AM PM		AM PM
29			AM PM		AM PM

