**APPENDIX J: CYP1A2, CYP2C8, CYP2C19, CYP3A4 SUBSTRATES, INHIBITORS & INDUCERS \***

SUBSTRATE(S)				
1A2	2C8	2C19	3A4	
amitriptyline caffeine clomipramine clozapine cyclobenzaprine duloxetine estradiol fluvoxamine haloperidol imipramine N-DeMe mexiletine naproxen olanzapine ondansetron phenacetin→ acetaminophen→NAP QI propranolol riluzole ropivacaine tacrine theophylline tizanidine triamterene verapamil (R)warfarin zileuton zolmitriptan	[paclitaxel] torsemide amodiaquine cerivastatin repaglinide sorafenib	Proton Pump Inhibitors (PPIs): esomeprazole lansoprazole omeprazole pantoprazole rabeprazole  Anti-epileptics: diazepam→Nor phenytoin(O) S-mephenytoin phenobarbitone  amitriptyline carisoprodol citalopram chloramphenicol clomipramine chlopidogrel cyclophosphamide hexobarbital imipramine N-DeMe indomethacin labetalol R-mephobarbital moclobemide nelfinavir nilutamide primidone progesterone proguanil propranolol teniposide R-warfarin→8-OH voriconazole	Macrolide antibiotics: clarithromycin erythromycin (not 3A5) NOT azithromycin telithromycin  Anti-arrhythmics: quinidine→3OH (not 3A5)  Benzodiazepines: alprazolam diazepam→3OH midazolam triazolam  Immune Modulators: cyclosporine tacrolimus (FK506)  HIV Antivirals: indinavir nelfinavir ritonavir saquinavir  Prokinetic: cisapride  Antihistamines: astemizole chlorpheniramine terfenadine  Calcium Channel Blockers: amlodipine diltiazem felodipine lercanidipine nifedipine nisoldipine nitrendipine verapamil  HMG CoA Reductase Inhibitors: atorvastatin cerivastatin	Steroid 6beta-OH: estradiol hydrocortisone progesterone testosterone  Miscellaneous: alfentanil aprepitant aripiprazole boceprevir buspirone carbamazepine cafergot caffeine→TMU cilostazol cocaine codeine-N-demethylation dapsone dexamethasone dextromethorphan docetaxel domperidone eplerenone fentanyl finasteride gleevec haloperidol irinotecan LAAM lidocaine methadone nateglinide nevirapine ondansetron pimozide propranolol quetiapine quinine risperidone romidepsin NOT rosuvastatin salmeterol sildenafil sirolimus sorafenib

SUBSTRATE(S)			
1A2	2C8	2C19	3A4
			lovastatin NOT pravastatin NOT rosuvastatin simvastatin  tamoxifen taxol telaprevir terfenadine torisel trazodone vemurafenib vincristine zaleplon ziprasidone zolpidem

INHIBITORS			
1A2	2C8	2C19	3A4

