fluvoxamine ciprofloxacin cimetidine amiodarone efavirenz fluoroquinolones fluvoxamine furafylline interferon methoxsalen mibefradil ticlopidine	gemfibrozil trimethoprim glitazones montelukast quercetin	PPIs: Esomeprazole lansoprazole omeprazole pantoprazole  Other: rabeprazole chloramphenicol cimetidine felbamate fluoxetine fluvoxamine indomethacin ketoconazole modafinil oral contraceptives oxcarbazepine probenecid ticlopidine topiramate voriconazole	HIV Antivirals: indinavir nelfinavir ritonavir clarithromycin itraconazole ketoconazole nefazodone saquinavir telithromycin aprepitant erythromycin fluconazole grapefruit juice verapamil diltiazem cimetidine amiodarone NOT azithromycin Chloramphenicol boceprevir ciprofloxacin delaviridine diethyldithiocarbamate fluvoxamine gestodene imatinib mibefradil mifepristone norfloxacin norfluoxetine star fruit telaprevir voriconazole

INDUCERS			
1A2	2C8	2C19	3A4
broccoli brussel sprouts carbamazepine char-grilled meat insulin methylcholanthrene modafinil nafcillin beta-naphthoflavone omeprazole rifampin tobacco	rifampin	carbamazepine nevirapine phenobarbital rifampin secobarbital St. John's Wort	HIV Antivirals: efavirenz nevirapine barbiturates carbamazepine glucocorticoids modafinil oxcarbazepine phenobarbital phenytoin pioglitazone rifabutin rifampin St. John's wort troglitazone

\*Reference: <http://medicine.iupui.edu/clinpharm/ddis/main-table/>

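### Section 10.2 names diltiazem as a first-step drug for axitinib-related hypertension, without a caution, although Appendix J lists it as a CYP3A4 inhibitor and axitinib is cleared mainly by CYP3A4/5

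*Combined protocol and SAP*

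**What the plan says.** Section 10.2, under management of axitinib-related hypertension, tells sites to start and increase antihypertensives briskly and sets an order of preference. The first step is "Calcium channel blockers: (amlodipine, nifedipine, diltiazem, etc"; the second is ACE inhibitors or ARBs; the third is diuretics. The drugs it says to avoid are beta-blockers, clonidine and digoxin. It does not mention CYP3A4.

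Elsewhere the protocol treats that enzyme as important for this drug:

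- Section 9.1.3: "Axitinib is metabolized primarily in the liver by CYP3A4/5".
- Appendix J, 3A4 column of the inhibitor table: "grapefruit juice verapamil diltiazem cimetidine amiodarone".
- Appendix J, 3A4 substrates, calcium channel blockers: "amlodipine diltiazem felodipine lercanidipine nifedipine nisoldipine nitrendipine verapamil".
- Section 8.4.1, in its paragraph on strong inhibitors: "Selection of an alternate concomitant medication with no or minimal CYP3A4/5 inhibition potential is recommended". If a strong inhibitor cannot be avoided, it recommends roughly halving the axitinib dose. It allows CYP3A4/5 substrates at the physician's discretion.
- Section 8.4.1, in general: "The PI should be alerted if the patient is taking any agent known to affect or with the potential to affect selected CYP450 isoenzymes".
- Appendix I, directions to patients: "Avoid taking grapefruit juice".
- Section 5.2, exclusion 13, covers "medications that may affect the metabolism of pembrolizumab and/or axitinib within 7 days prior to Cycle 1", and section 8.7 carries specific prohibitions in the exclusion criteria into the treatment period.

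**The concern.** The step meant to control an axitinib toxicity names a drug that the protocol's own reference table lists as inhibiting the enzyme that mainly clears axitinib. If diltiazem raises axitinib exposure, treating the hypertension in this way could add to its cause.

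The step is likely to be used. Section 9.1.4 reports hypertension in 145 of 359 patients (40%) on axitinib in the renal cell trial, with median onset within the first month. Section 1.3 reports grade 3/4 hypertension in 7 of 60 patients in the axitinib sarcoma trial.

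The dose rules may not respond quickly to added exposure that shows itself as blood pressure. Section 10.2 lowers axitinib for blood pressure only when it stays at or above 150/100 on maximal doses of three drugs. The footnote to Table 10 limits the toxicities that drive titration to oral mucositis, diarrhea, hand-foot syndrome and fatigue. On that reading, a patient taking diltiazem for hypertension could still have axitinib escalated.

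**Working it through.** No power, alpha or event count is involved. The check compares sections and makes two counts.

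**1. Does 10.2 name diltiazem without a caution?** Yes. It is the third of three examples in the first step. The list of drugs to avoid does not include it, and there is no reference to 8.4.1 or Appendix J.

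**2. Does the protocol link diltiazem to axitinib clearance?** Yes, through two statements: the main route is CYP3A4/5 (9.1.3), and diltiazem inhibits 3A4 (Appendix J). Appendix J does not grade strength.

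**3. How much of the 10.2 sequence is affected?** The named drugs are amlodipine, nifedipine, diltiazem, lisinopril, valsartan, losartan, hydrochlorothiazide and furosemide: 3 + 3 + 2 = 8. In the Appendix J 3A4 inhibitor list: diltiazem only, so 1 of 8.

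**4. What alternatives remain in the class?** Appendix J lists 8 calcium channel blockers as 3A4 substrates: amlodipine, diltiazem, felodipine, lercanidipine, nifedipine, nisoldipine, nitrendipine and verapamil. Diltiazem and verapamil are also in the inhibitor list, so 8 − 2 = 6 remain. Two of the six, amlodipine and nifedipine, are already on the 10.2 line.

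**5. Does another rule settle the matter?**

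| Provision | Covers diltiazem? |
|---|---|
| 8.4.1, strong inhibitors | Not shown: diltiazem is not among the 11 examples |
| 8.4.1, weaker inhibitors | No rule given, although moderate inducers do have one |
| 8.4.1, PI alert | Yes, as an agent that may affect a CYP450 isoenzyme, but 10.2 does not refer to it |
| 8.4.1, substrates allowed | Diltiazem is listed as a substrate, but this does not address inhibition |
| Exclusion 13 with 8.7 | Uncertain: it names no drug and sets a 7-day window before treatment, and 8.7 extends only specific prohibitions |
| Appendix I, grapefruit juice | Not about diltiazem, but grapefruit juice is in the same Appendix J inhibitor list |

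In the text available, the PI alert is the only provision that clearly reaches diltiazem. It asks for notification and sets no avoidance or dose rule.

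**The case against.** The strongest reply is that no rule is broken. Section 8.4.1 restricts strong inhibitors and does not call diltiazem one; its sentence on choosing alternatives sits in the strong-inhibitor paragraph. Appendix J is an ungraded reference table with no action attached. Cimetidine is in the same inhibitor column, yet the patient diary permits it after discussion with the doctor (its stated concern there is absorption). Diltiazem is the last of three examples, is not mandated, and would be prescribed with home blood pressure readings and a PI alert in place. Section 8.5.1 on acceptable medications leaves necessary treatment to the investigator. Appendix E, which 8.4.1 cites for axitinib interactions, was not available to this review and may give further guidance. The size of any interaction is not in the documents.

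Most of this stands. No breach of the strong-inhibitor rule is shown, exclusion 13 is weak support at best, and harm cannot be quantified. None of it changes the wording of 10.2, which recommends the drug, has its own list of drugs to avoid, and sends the reader nowhere else. A clinician is less likely to raise an alert about a drug the protocol itself suggests. The revision history for version 3.0 also records an intention that inhibitors be avoided while substrates are allowed, which points the same way.

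**Conclusion.** The point holds as a minor inconsistency with a safety aspect. Section 10.2 suggests, for an axitinib toxicity, a drug that Appendix J lists as an inhibitor of axitinib's main metabolizing enzyme, and adds no caution. It affects 1 of the 8 drugs named there, and two calcium channel blockers on the same line carry no inhibitor listing.

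The conclusion rests on Appendix J and section 9.1.3 as written. It assumes no particular strength of inhibition, change in exposure or rate of diltiazem use. Appendix E could lessen the practical risk, as the PI alert already does. No effect on the primary endpoint is claimed.

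**What to change.** In section 10.2, replace the bracketed examples after calcium channel blockers with:

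*(e.g. amlodipine, nifedipine). Avoid diltiazem and verapamil, which are CYP3A4 inhibitors (Appendix J); if either is considered necessary, alert the PI first (see 8.4.1).*

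Verapamil is included because the existing list is open-ended and Appendix J gives verapamil the same inhibitor listing.

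The cost is one line of protocol wording and two fewer calcium channel blockers for routine use. The other 6 of the 8 in Appendix J and the ACE inhibitor/ARB and diuretic steps are unchanged, and either discouraged drug can still be used after contact with the PI.

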**Table 10. Dose Titration of Axitinib**

a Dosing modifications based only on the following grade 2 toxicities: oral mucositis, diarrhea, hand-foot syndrome, fatigue. Dose modifications for other drug-related AEs as per table below and as per study principal investigator. CTC v4 definitions of grade 2 toxicities:

Oral mucositis: Moderate pain; not interfering with oral intake; modified diet indicated

Diarrhea: Increase of 4 - 6 stools per day over baseline

HFS: Skin changes (e.g., peeling, blisters, bleeding, edema, or hyperkeratosis) with pain; limiting instrumental ADL

Fatigue: Fatigue not relieved by rest; limiting instrumental ADL

b After dose reduction, re-escalation as tolerated may be considered per provider discretion

Toxicity	Grade:	Treatment	Dose reduction
Hypertension/ Hypertensive crisis  (Defined as $\geq$ 150/100 or symptoms such as headache, chest pressure, blurry vision)	2	Add appropriate anti-hypertensive medications	No dose reduction required
	3	Add appropriate anti-hypertensive medications	If persistent despite 3 or more medications and associated with persistent symptoms, dose reduce one level
	4	Discontinue axitinib	Discontinue axitinib
Thrombotic events (arterial)	2-4	Discontinue axitinib	Discontinue axitinib
Thrombotic events (venous) – uncomplicated DVT/PE	3	Provide anticoagulation	No dose adjustment required
Other venous thromboembolic disease (ie retinal vein occlusion)	3	Consider discontinuation of axitinib	Consider discontinuation of axitinib
Hemorrhage	2	Hold axitinib until resolution to $\leq$ grade 1	Dose reduce one dose level

	3	Hold axitinib until resolution to $\leq$ grade 1	Dose reduce one dose level. Discontinue if recurs with restarting medication.
	4	Discontinue axitinib.	Discontinue axitinib.
Thyroid dysfunction	2	Treat with replacement/suppression	No dose change
	3	Treat with replacement/suppression. Hold axitinib until resolution to $\leq$ grade 1. *refer to pembrolizumab dose modifications for additional treatment	Dose reduce one dose level
	4	Discontinue axitinib	Discontinue axitinib
Reversible posterior Leukoencephalopathy Syndrome	2-4	Discontinue axitinib	Discontinue axitinib
Proteinuria	2	Continue treatment if asymptomatic and not associated with creatinine rise. If accompanied by renal insufficiency or evidence of nephritis, refer to pembrolizumab guidelines for treatment and hold axitinib until $\leq$ grade 1.	If isolated proteinuria, no dose reduction. If associated with AKI/nephritis, dose reduce one dose level after resolution to $\leq$ grade 1.
	3	Hold axitinib until $\leq$ grade 1. Refer to pembrolizumab guidelines as per grade 2.	Dose reduce one dose level
Elevation of liver enzymes or bilirubin	2/3	Hold axitinib until $\leq$ grade 1. *	Dose reduce one dose level.
	4	Discontinue axitinib	Discontinue axitinib.
Other toxicity	2	Intolerable grade 2 toxicity, may hold axitinib or dose-reduce at physician discretion.	May hold axitinib or dose-reduce at physician discretion.
	3	Hold until resolution to $\leq$ grade 1	Dose reduce one dose level.
	4	Discontinue axitinib	Discontinue axitinib.

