#### 9.1.4 Management of Agent-Specific Adverse Events

##### Hypertension and Hypertensive Crisis

In a controlled clinical study with INLYTA for the treatment of patients with RCC, hypertension was reported in 145/359 patients (40%) receiving INLYTA and 103/355 patients (29%) receiving sorafenib. Grade 3/4 hypertension was observed in 56/359 patients (16%) receiving INLYTA and 39/355 patients (11%) receiving sorafenib. Hypertensive crisis was reported in 2/359 patients (<1%) receiving INLYTA and none of the patients receiving sorafenib. The median onset time for hypertension (systolic blood pressure >150 mmHg or diastolic blood pressure >100 mmHg) was within the first month of the start of INLYTA treatment and blood pressure increases have been observed as early as 4 days after starting INLYTA. Hypertension was managed with standard antihypertensive therapy. Discontinuation of INLYTA treatment due to hypertension occurred in 1/359 patients (<1%) receiving INLYTA and none of the patients receiving sorafenib.

Blood pressure should be well-controlled prior to initiating INLYTA. Patients should be monitored for hypertension and treated as needed with standard anti-hypertensive therapy. In the case of persistent hypertension despite use of anti-hypertensive medications, reduce the INLYTA dose. Discontinue INLYTA if hypertension is severe and persistent despite anti-hypertensive therapy and dose reduction of INLYTA, and discontinuation should be considered if there is evidence of hypertensive crisis. If INLYTA is interrupted, patients receiving antihypertensive medications should be monitored for hypotension.

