## 10.0 TREATMENT/ DOSE MODIFICATIONS

### 10.1 Unacceptable Toxicity

Causality for all adverse events should be assessed and if deemed attributable, attempts should be made to attribute to either axitinib, pembrolizumab, or potentially both agents.

In the case of toxicities refractory to routine medical management which are assessed as possibly attributable to both drugs (i.e. liver enzyme elevation, renal dysfunction, thyroid dysfunction, diarrhea/colitis) that may be autoimmune in origin, dose interruption of axitinib should be attempted first. Generally prompt resolution of the toxicity is observed if attributable to axitinib. If the toxicity is persistent, treatment should be administered as per the pembrolizumab treatment guidelines below, including corticosteroid therapy where advised.

Drug-related grade 4 toxicities will generally require subject to discontinue all study treatment. Exceptions include the following: 1) clear evidence that the toxicity was attributable to axitinib alone, resolved upon cessation of axitinib, and there is rationale to continuing pembrolizumab monotherapy 2) Grade 4 lab abnormalities that are not immune-related, where the patient is asymptomatic, and the abnormalities can be reversed with medical treatment. Example: grade 4 hypertriglyceridemia that responds to antilipid drugs. Intolerable grade 2 and grade 3 toxicities should be managed as per dose modification guidelines listed in the tables below. For grade 2 and grade 3 toxicities attributable to axitinib that do not resolve to  $\leq$  grade 1 within 3 weeks of holding study drug, axitinib should be permanently discontinued. Pembrolizumab therapy may be continued providing the residual adverse events are within permissible ranges for pembrolizumab dosing.

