**Table 11. Additional Dose Modification Guidelines for Axitinib.**

\*NOTE: if patient starts with grade 2 LFT elevation (liver metastases), any increase of  $\geq$  to 50% of baseline that does not resolve within 7 days is considered grade 3 toxicity and patients should be dose reduced as above.

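### The Table 11 grade 3 hypertension cell ties axitinib reduction to persistent symptoms, a condition absent from sections 10.2 and 9.1.4, and no text says which rule governs

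*Combined protocol and SAP*

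**What the plan says.** Three places in the combined protocol and SAP say when to lower axitinib for hypertension that does not respond to treatment.

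- **Section 10.2, management of axitinib-related hypertension.** If blood pressure is still at or above 150/100 mm Hg "despite maximal doses of three anti-hypertensive medications, axitinib should be reduced by one dose level". Neither symptoms nor a toxicity grade is mentioned.
- **Section 9.1.4, hypertension and hypertensive crisis.** "In the case of persistent hypertension despite use of anti-hypertensive medications, reduce the INLYTA dose". Again there is no symptom condition.
- **Table 11, hypertension row, grade 3.** "If persistent despite 3 or more medications and associated with persistent symptoms, dose reduce one level".

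Two other passages direct the clinician to the tables. Section 10.1 says: "Intolerable grade 2 and grade 3 toxicities should be managed as per dose modification guidelines listed in the tables below". Footnote a of Table 10 says: "Dose modifications for other drug-related AEs as per table below and as per study principal investigator". The caption of the second table is "Table 11. Additional Dose Modification Guidelines for Axitinib". No sentence says whether the section 10.2 text or the Table 11 cell prevails when they differ.

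**The concern.** Hypertension is a known axitinib toxicity, and these are the instructions a treating clinician will use. Two of the three rules call for a lower dose on blood pressure and treatment history alone. The third, in the table to which the clinician is sent, adds persistent symptoms. A patient whose pressure stays high on three maximally dosed drugs but who feels well meets the section 10.2 rule and not the table's trigger. If the table is read on its own, that patient may stay at the current axitinib level.

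The symptom condition also fits poorly with the rest of the plan. The same Table 11 row defines the event as pressure at or above 150/100 or symptoms, so there symptoms are an alternative and not a requirement. The grade 3 rows for thyroid dysfunction, proteinuria, liver tests and other toxicity reduce one level without asking for symptoms. Section 9.1.4 makes discontinuation for severe persistent hypertension a step that follows a dose reduction; under the table alone, the asymptomatic patient does not reach the first step.

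**Working it through.** No design figure (power, alpha, sample size) is involved. The check sets the rules side by side and then sizes the dose difference.

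**1. The two section 10 triggers.** Take a grade 3 patient with pressure still at or above 150/100 mm Hg on three drugs.

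| Drug doses | Symptoms | Section 10.2 | Table 11, grade 3 |
|---|---|---|---|
| maximal | none | reduce one level | trigger not met |
| maximal | persistent | reduce one level | reduce one level |
| not maximal | persistent | trigger not met | reduce one level |
| not maximal | none | trigger not met | trigger not met |

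Only the first row is a safety gap. In the third row Table 11 adds a reduction, which is the cautious direction.

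**2. Section 9.1.4.** It requires neither three drugs nor maximal doses, so it is broader than section 10.2. It is used here only to show that the symptom condition has no counterpart in it.

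**3. Size per patient.** The difference is one step on the Table 3 dose ladder, as a share of the current BID dose:

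- 10 to 8 mg: 2/10 = 20%
- 8 to 7 mg: 1/8 = 12.5%
- 7 to 6 mg: 1/7 = 14.3%
- 6 to 5 mg: 1/6 = 16.7%
- 5 to 4 mg: 1/5 = 20%
- 4 to 3 mg: 1/4 = 25%
- 3 to 2 mg: 1/3 = 33.3%

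At 2 mg BID there is no lower level, and the next step in Table 10 is to stop axitinib.

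**4. How many patients.** The documents give no rate of refractory, asymptomatic grade 3 hypertension. They do give grade 3/4 hypertension of any kind: 7/60 in the axitinib sarcoma trial (section 1.3) and 56/359 in the renal cell trial (section 9.1.4). If those rates applied to the 40 evaluable patients of section 16.4, which is an assumption, the expected numbers would be 40 × 7/60 = 4.7 and 40 × 56/359 = 6.2. Only a subset would be both refractory and asymptomatic. Section 9.1.4 also reports: "Discontinuation of INLYTA treatment due to hypertension occurred in 1/359 patients (<1%) receiving INLYTA". That is 1/359 = 0.28%. It is not a rate of refractory hypertension, but it suggests that the case is uncommon.

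**5. When it matters.** In cycle 1 (49 days, section 7.2), grade 3 hypertension that cannot be controlled within 7 days is a DLT with or without symptoms (Table 5), and section 11.0 lists a DLT as a reason for which treatment may be stopped. Section 10.2 makes escalation at cycle 2 day 1 conditional on there being no grade 2 or greater toxicity. After that the scheduled checks thin out. From cycle 3 the calendar in section 12.7 places vital signs on day 1 of each six-week cycle, and blood pressure logs are tied to dose changes (section 8.5.1 and calendar note H). In axitinib monotherapy the cycles are 12 weeks long and visits may be by telehealth (sections 8.0 and 12.2.18).

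**The case against.** The strongest answer is that Table 11 is silent and does not contradict section 10.2. The cell says when to reduce; it does not say that the dose must otherwise be kept. Where the table means no reduction it says so, as in the grade 2 cell: "No dose reduction required". Section 10.2 joins its own guidelines and the tables with the word and, Table 11 is captioned as additional, and the tables sit within section 10.2, just after the hypertension bullets. Read together, the two rules mean that either trigger suffices, and the asymptomatic patient is reduced. Footnote a also brings in the principal investigator, and section 11.0 allows treatment to stop for any adverse event that the investigator judges an unacceptable risk.

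Most of this stands. The cumulative reading is plausible and gives the right action. It is not stated, however, and both section 10.1 and footnote a point to the tables without referring back to the hypertension bullets. The section 11.0 safeguard is discretionary and concerns stopping treatment, not lowering the dose.

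A reader might go further in three ways that the documents do not support:

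- That Table 11 forbids reduction in an asymptomatic patient, or orders the opposite of section 10.2. It does neither.
- That the patient is held at full dose. The patient stays at the current level, which may be anywhere from 2 to 10 mg BID.
- That the grade 2 cell conflicts with section 10.2 in the same way. The section 10.2 rule names no grade, but whether a patient on three maximally dosed drugs could still be grade 2 depends on the CTCAE grading of hypertension, which the documents do not reproduce.

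**Conclusion.** The point holds as an inconsistency in a safety instruction and should be fixed. A clinician who applies Table 11 alone may leave an asymptomatic patient with refractory grade 3 hypertension at the current axitinib level, although section 10.2 orders a one-level reduction and section 9.1.4 also calls for a lower dose. A clinician who reads section 10.2 and Table 11 together would reduce.

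The consequence is limited. It is one dose level per affected patient, in a case that is probably uncommon and arises mainly after cycle 1. The number of patients cannot be estimated from the documents. The DLT definition has no symptom condition, so DLT counts and the safety stopping table do not change, and neither does the PFS analysis. The conclusion rests on the wording as it stands and on the absence of any precedence rule; it does not assume that clinicians will in fact read the table in isolation.

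Section 10.2 also still cites Tables 8 and 9, which are now the pembrolizumab re-introduction schema and the regimen description. That is a clerical slip and is not evidence for the dosing point.

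**What to change.** Reword the Table 11 grade 3 hypertension cell along these lines: *reduce axitinib by one level if blood pressure is still ≥ 150/100 mm Hg with three antihypertensives each at maximal dose, whether or not the patient has symptoms, or if symptomatic hypertension persists on three or more antihypertensives.* Use the same trigger in the section 10.2 hypertension bullet, so that the question of precedence does not arise.

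As an editorial correction in the same amendment, change the section 10.2 references from Tables 8 and 9 to Tables 10 and 11.

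The cost is one table cell, one bullet and the table numbers. The downside is possibly a few more one-level reductions. Section 10.2 largely already requires these, and footnote b of Table 10 lets the provider consider re-escalation as tolerated.
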